5.6 Further analyses

5.6.1 Sensitivity analyses

Different sensitivity analyses can be planned to take into account:

- 1. the effect of vaccine related serotypes (that gives cross-protection or not) by including these serotypes in the control group.
- 2. excluding the vaccinated <14 days.
- 3. vaccinated with PPSV23 more than x years ago (e.g. 10 years) considered unvaccinated.
- 4. missing vaccination status by considering individuals with missing vaccination status:
 - unvaccinated;
 - vaccinated;
 - imputed according the available predictors.

Taking into account uncertain vaccination status: to help determine if no record of vaccination mean unvaccinated, some sites might obtain the date of registration with the general practice. This will allow to run a sensitivity analysis including those registered with the general practice in the last x years (to be determined).

► Each study site to describe the sensitivity analyses planned.

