4.6 Exposure

4.6.1 Definition of vaccination status

- Unvaccinated: absence of records of vaccination with PCV13 or PPSV23 in the vaccination registry or medical records, or if the vaccine dose was given less than 14 days prior to onset of symptoms;
- Vaccinated with PCV13: individuals that have received at least one dose PCV13 at least 14 days before onset of symptoms;
- Vaccinated with PPSV23: individuals who have received at least one dose of PPSV23 at least 14 days before onset of symptoms regardless the age and time since vaccination;

TECHNICAL DOCUMENT – Protocol on effectiveness of Pneumo vaccines in elderly

- Vaccinated with both PCV13 and PPSV23: individuals who have received both vaccines, the last one received at least 14 days before onset of symptoms, regardless the age and time since vaccination with the first provided vaccine;
- Repeated vaccination with PPV23: individuals who received more than one dose of PPV23, the
 last one at least 14 days before onset of symptoms regardless the age and time since
 vaccination;
- Uncertain vaccination history: individuals with no vaccination information available (no written
 medical records or no registry available, brand name not mentioned, date of administration
 unknown) or vaccinated during a clinical trial.

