4.6.2 Vaccination status ascertainment

The exposure of interest in this study is the history of vaccination with any of PPSV23 or PCV13 vaccines. The vaccination history includes number of doses, date of administration of each dose and brand of each vaccine.

Vaccination status is extracted from available data sources: vaccination registry, hospital or family physicians medical records, or vaccination cards. Efforts should be made to validate the vaccination status. Information on individuals with no information on vaccination status is collected and considered for the sensitivity analysis.

► Each study site to describe the quality and source of the vaccination data and whether they plan to validate the vaccination ascertainment using other sources or studies (vaccination survey, etc.).

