5.3 Measure of association

Vaccine effectiveness will be computed as 100% X (1 – the odds of vaccination in VT cases / odds of vaccination in NVT controls). An exact 95% confidence interval will be computed around the point estimate. The crude and adjusted estimates of vaccine effectiveness will be provided.

The VE will be computed for all exposures mentioned above.

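### As worded, the optional GP-registration sensitivity analysis keeps recent registrants, so it cannot check whether no vaccination record means unvaccinated

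*Protocol*

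**What the plan says.** Three parts of the protocol bear on this point.

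- **The rule under test (section 4.6.1).** A patient is unvaccinated on "absence of records of vaccination with PCV13 or PPSV23 in the vaccination registry or medical records". A dose given less than 14 days before onset is also treated as no vaccination.
- **The look-back (section 4.6.1).** PPSV23 exposure is "at least one dose of PPSV23 at least 14 days before onset of symptoms regardless the age and time since vaccination". An old dose counts as fully as a recent one.
- **The check (section 5.6.1).** The stated purpose is: "to help determine if no record of vaccination mean unvaccinated, some sites might obtain the date of registration with the general practice". The analysis is then described: "This will allow to run a sensitivity analysis including those registered with the general practice in the last x years (to be determined").

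On sources, section 4.6.2 says: "Vaccination status is extracted from available data sources: vaccination registry, hospital or family physicians medical records, or vaccination cards". How far a site depends on practice records therefore varies. No other section describes the registration-date analysis, and none asks for a minimum length of registration.

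**The concern.** The absence of a record is evidence of non-vaccination only if the record reaches back far enough to have shown a dose. Because PPSV23 counts however long ago it was given, the record must reach back many years. Another sensitivity analysis in section 5.6.1 uses 10 years as its example of a long interval since PPSV23, so doses that old are expected.

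A patient who joined the practice recently may have been vaccinated under an earlier one. If status is read from practice records, that dose may not appear and the patient is counted as unvaccinated. Selecting on a recent registration date then gathers the patients in whom the rule is least believable and leaves out those in whom it is most believable.

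At stake is the interpretation of the main result. A lower VE in the selected subset could come from poorer records there, yet be read as doubt about the whole-sample estimate. The protocol is a template for several countries and a pooled article is planned (section 8), so sites could also run opposite selections under the same label.

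**Working it through.** The protocol gives no figure for this analysis, and x is left open, so there is no stated number to reproduce. The direction follows from the text; the size needs assumptions.

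**Inputs**
- Effect measure, section 5.3: "Vaccine effectiveness will be computed as 100% X (1 – the odds of vaccination in VT cases / odds of vaccination in NVT controls").
- Coverage in controls, p0: 10% to 70%, the range in Table 4 of section 4.8.
- True VE: 60%, the average quoted for PPSV23 against vaccine-type IPD in section 1.1. Values of 30% and 90% were also tried, within the 20% to 90% planning range of section 4.8.
- Record sensitivity s, the share of true doses that appear in the record: **assumed**. Here 0.95 stands for long registration and 0.7 to 0.5 for recent registration. The documents give no value.
- Also assumed: no false records of vaccination, and the same s in cases and controls.

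**Formulas**
- True coverage in cases, p1: odds(p1) = (1 − VE) × odds(p0).
- Observed VE = 1 − [s·p1/(1 − s·p1)] / [s·p0/(1 − s·p0)].
- Share of no-record controls who were in truth vaccinated = p0(1 − s)/(1 − s·p0).

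**Worked case, VE 60%, p0 = 0.70, s = 0.5**
- odds(p0) = 0.70/0.30 = 2.333; odds(p1) = 0.4 × 2.333 = 0.933; p1 = 0.483.
- Recorded coverage: controls 0.350, cases 0.241.
- Recorded odds: controls 0.538, cases 0.318.
- Observed VE = 1 − 0.318/0.538 = 40.9%.

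**Worked case, VE 60%, p0 = 0.10, s = 0.5**
- odds(p0) = 0.1111; odds(p1) = 0.0444; p1 = 0.0426.
- Recorded odds: controls 0.05/0.95 = 0.0526, cases 0.0213/0.9787 = 0.0217.
- Observed VE = 1 − 0.0217/0.0526 = 58.7%.

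**Observed VE when true VE is 60%**

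| Coverage | s = 1 | s = 0.95 | s = 0.7 | s = 0.5 |
|---|---|---|---|---|
| 10% | 60.0% | 59.9% | 59.2% | 58.7% |
| 30% | 60.0% | 59.5% | 57.1% | 55.3% |
| 50% | 60.0% | 58.8% | 53.6% | 50.0% |
| 70% | 60.0% | 57.3% | 46.9% | 40.9% |

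**Share of no-record controls who were in truth vaccinated**

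| Coverage | s = 0.95 | s = 0.7 | s = 0.5 |
|---|---|---|---|
| 10% | 0.6% | 3.2% | 5.3% |
| 30% | 2.1% | 11.4% | 17.6% |
| 50% | 4.8% | 23.1% | 33.3% |
| 70% | 10.4% | 41.2% | 53.8% |

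The direction was the same in every combination tried. With s = 0.5, a true VE of 30% becomes 28.9% at 10% coverage and 16.5% at 70%; a true VE of 90% becomes 89.5% and 80.6%.

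**The case against.** **The sentence may only be loose English.** It could mean registered throughout the last x years, which is the sensible analysis and fits the stated purpose. It could also mean adding a group back: the first item of section 5.6.1 uses the same verb for adding serotypes to the control group. Both readings are possible, and a drafting slip is plausible. A reader might infer that the authors deliberately chose the wrong patients; the documents do not show that. But the variable is a date of registration, the words select a recent one, and nothing elsewhere corrects them. On any reading the sentence needs rewording.

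**Recent registrants need not have poorer records.** The protocol nowhere says they do. The inference is reasonable where status comes from practice records and weaker where a population registry, vaccination cards or transferred records are used. This stands, and it limits the point to sites of the first kind.

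**Looking where the rule is weakest can be informative.** A contrast between recent and long registrants could be. The text describes only one group, however, with no comparison group whose records are credible. A shift could then reflect missing doses or a real difference between patients.

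**The effect may be small.** This is true at low coverage: 1.3 points (60.0 − 58.7) at 10% coverage even with half the doses missed. At 70% coverage it is 19.1 points (60.0 − 40.9).

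**Other safeguards exist.** Section 4.6.2 asks for efforts to validate vaccination status, and section 6.2.3 asks sites to discuss ascertainment bias. These stand. The analyses of missing status in section 5.6.1 do not fill the gap, because a patient without a record in an available source is classed as unvaccinated, not missing.

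**Conclusion.** Wrong as written. The selection runs against the purpose given in the sentence before it. At sites relying on practice records it would gather under-recorded patients, and so could not show whether no record means unvaccinated.

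Under equal under-recording in cases and controls, with no false records, the direction is toward zero. The size is not fixed by the documents: it depends on assumed record completeness and on coverage, and runs from negligible to large over the protocol's own coverage range.

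A reader might go further and infer that the main VE estimate is biased by this sentence. It is not. The analysis is optional, is secondary, depends on a date that only some sites may obtain, and does not enter the primary estimate. Leaving x open is likewise no fault in a generic protocol; the fault is which side of x is kept.

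**What to change.** Replace the sentence in section 5.6.1 with: *a sensitivity analysis restricted to those registered with the general practice for at least x years before onset*. Each site should set x so that it covers the relevant look-back for PPSV23 in its setting, and state it in the site protocol.

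The cost is one sentence. No data are needed beyond the registration date that the analysis already presupposes, though collecting that date remains optional. The restricted set loses recent movers, so its interval will be slightly wider. The primary analysis does not change.

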5.6.2 Time since vaccination

Where sample size allows, further analyses will be carried out to explore the duration of protection. VE by time since vaccination will be computed. Time since vaccination can be calculated by subtracting the date of vaccination from the date of onset/diagnosis/notification and it can then be modelled as a continuous variable. Otherwise the analysis can be done, if sample size permit by several categories: vaccination within <2 years, ≥5 years.

6. Limitations

6.1 Assessment of bias due to replacement in the indirect cohort method

Andrews et al examined the bias introduced by the complete replacement when using the indirect cohort method when the true PCV effectiveness (VE) is 70% and 90%, for different levels of VE against carriage (VEc) and proportion of carriage of vaccine serotypes in the unvaccinated (Pu). The formula relating these parameters is:

 $VE_{Broome} = 1 - (1-VE)/(1 + VEc Pu / (1-Pu))$

where: VE= true vaccine effectiveness, VEc = vaccine effectiveness against acquisition of the vaccine serotype in the nasopharynx, Pu=proportion of carriage of vaccine serotypes in unvaccinated.

Bias increases as VEc increases and with increasing Pu (Figure 2). Data on acquisition of vaccine serotype in nasopharynx is not available and difficult to be obtained, therefore data available on carriage prevalence was used by Andrews et al to calculate the VEc. Considering an average Pu=40% and a VEc=50%, the calculated VE_{Broome} will be 92.5% when the true VE is 90%. For a true VE of 70%, and a VEc

of 30%, the VE_{Broome}= 75%. The authors concluded that a realistic range of bias using UK data is around 2-5%. However this assumption should be investigated for the specific site situations.

In a study using CDC's ABCs data, De Serres et al simulated the VE estimates when changing the ratio of an increase in NVT among vaccinated and unvaccinated children (Figure 3). The authors concluded that the VE results are not biased if the change in NVT affects equally (proportional increase) vaccinated and unvaccinated children. The most likely scenario presented for USA was the increase in incidence of NVT of 150% greater in vaccinated than unvaccinated children, as the vaccination coverage was ≥90% for PCV7. In this scenario, the absolute overestimation was judged minimal (2%) for a true VE of 95% and reasonable (10%) for a true VE of 70%. However, the authors stated that in a setting where vaccine is provided only to high-risk children who are at increased risk for NVT disease compared to healthy children, VE estimates using the indirect cohort method will be less reliable and is not recommended.

[figure not shown]

Figure 2: Assessment of bias with the indirect cohort method when assuming complete serotype replacement (from Andrews et al 2012).

[figure not shown]

Figure 3: Assessment bias with the indirect cohort method using different scenarios (from De Serres et al 2011).

6.2 Limitations related to different aspects of the study

6.2.1 Study population

► Each study site to describe the limitations related to the representativeness of the study population and thus the generalisability of the results.

6.2.2 Database(s) quality, validity

► Each study site to describe the data quality in the surveillance database or other sources used for vaccine effectiveness analysis. If variables in the database used has not been validated, the possibility of validating the information using other data sources should be addressed.

6.2.3 Exposure, vaccination status

► Each study site to describe any potential bias related to ascertainment of vaccination status, ways to minimise the bias and how bias can affect the estimates.

6.2.4 Outcome

► Each study site to describe any potential bias related to the outcome used and the way the outcome is ascertained.

6.2.5 Control group

► Each study site to describe the limitations related to the use of the IPD/SpCAP cases due to non-vaccine serotypes as reference group (i.e. do reference group represent the vaccination coverage of the population giving rise to the IPD/SpCAP cases due to vaccine serotypes?).

6.2.6 Selection bias

► Each study site to describe any selection bias that may occur in the selection of individuals to be tested for an IPD or SpCAP. Testing is frequently related to the clinical presentation and the severity of the disease, therefore the results will mainly reflect the effectiveness against these more severe diseases. Also, a

TECHNICAL DOCUMENT – Protocol on effectiveness of Pneumo vaccines in elderly

selection bias may occur if testing is done differentially according to the vaccination status. In addition, increasing blood culturing and PCR testing over time should be also taken into account in the interpretation of the results.

6.2.7 Confounding

► Each study site to describe how they will minimise the effect of potential confounding factors and how residual confounding may affect the VE estimates.

6.2.8 Indirect effect of childhood vaccination

▶ It can be argued that the indirect effect of childhood vaccination will influence the effectiveness of the pneumococcal vaccines in the elderly, through the herd effect. However, if the random mixing of the population can be assumed, the herd effect affects equally the vaccinated and unvaccinated elderly, not biasing the effectiveness estimates. Study sites are invited to discuss how the indirect effect may influence the VE estimates in their settings if not random mixing can be assumed.

7. Ethical approval

► Each study site to describe the procedures to obtain the approval of the national / ethics committee.

8. Dissemination of results

Each study coordinator will decide where the results of the individual studies will be published and which scientific conferences will be attended in order to present the results. An article presenting the results of the pooled analysis and estimates for the EU/EEA will be submitted to a peer-reviewed journal. The list of authors will respect the recommendations of authorship stated by the International Committee of Medical Journal Editors http://www.icmje.org/ethical_1author.html. The actual authorship for the pooled article will be discussed and agreed with the study teams at the beginning of the study.

▶ Each study site to describe the plans to disseminate the results: preliminary reports, final report, publications.

9. Human resources

The roles and responsibilities of the members of the investigation team should be described: principal investigator, assistant, data manager, etc.

► Each study site to describe the team members' roles and responsibilities

Tables

Table 3: List of variables, coding, definitions and data sources, as collected in the IPD surveillance systems (harmonised under the SpIDnet/I-MOVE+project)

Variable name	Name of the variable in the site specific database	Variable label	Туре	Values and coding	Definition	Comments
siteid		Site identification	Unique ID	AAA	Surveillance site identification	
recordid		Record identification code	Unique ID	string	Surveillance unit identification and record identification code	
datenotif		Date of notification	Date	dd/mm/yyyy	Date when the case is notified the first time to the site level	
residence		Residence in the catchment area	Numeric	0-no 1-yes 9-unknown	Residence in the catchment area of the surveillance unit reporting to the system	
ageyears		Age of the case in years	Numeric	###	Age of patient in years as reported at the site level in years at time of hospital admission	

Variable name	Name of the variable in the site specific database	Variable label	Туре	Values and coding	Definition	Comments
sex		Gender	Code	0-female 1-male 9-unknown	Gender of the reported case	
dateadm		Date of the admission in the hospital	Date	dd/mm/yyyy	Date when the case was admitted to the hospital	
datedis		Date of the discharge from the hospital	Date	dd/mm/yyyy	Date when the case was discharged from the hospital	
outcome		Outcome	Code	0-alive 1-deceased 9-unknown	Information on survival at the end of hospitalisation: alive, deceased, unknown	
datedeath		Date of death	Date	dd/mm/yyyy	Date of death of the admitted patient (if outcome==1)	
clinic		Clinical entity	Multiple choice	0-unknown 1-meningitis 2-pneumonia 3- 4-bacteremia 5- 6- 9-other, specify	Clinical manifestation of the IPD case	This multiple-choice variable can be collected as such or each clinical entity can be entered separately using variables 12-20. If clinic =9, variable 20 (otherclin) specifies other

Variable name	Name of the variable in the site specific database	Variable label	Туре	Values and coding	Definition	Comments
						clinical entities of IPD not listed
meningitis		Pneumococcal meningitis	Code	0-no 1-yes 9-unknown	A case presenting with lab confirmed pneumococcal meningitis	
pneumonia		invasive pneumococcal pneumonia	Code	0-no 1-yes 9-unknown	A case presenting with lab confirmed pneumococcal pneumonia	
bacteremia		Bacteremia without known focus of infection		0-no 1-yes 9-unknown	A case presenting with lab confirmed bacteremia (blood stream infection) without known focus of infection	
otherclin		Other clinical entities	Text	String20	Other clinical entities of the IPD case	Please specify other clinical entity for the IPD cases
icuadm		Admission in the ICU	Code	0-no 1-yes 9-unknown	A lab confirmed case who needed admission in the ICU during the pneumococcal episode	
datediag		Date of diagnosis	Date	dd/mm/yyyy	Date when the diagnosis was made, should be the same with	

Variable name	Name of the variable in the site specific database	Variable label	Туре	Values and coding	Definition	Comments
					the identification/confirmation of the	
serotype		Serotype identified	Text	String3 PEN – pending NTP – non-typeable UKN - unknown	Serotype identified	
micpeni		MIC to penicillin	Numeric	##.###	MIC to penicillin in μg/ml	If not tested, the variable will be left blank
mic[macrolid]		MIC to macrolide	Numeric	##.##	MIC to macrolide in µg/ml [please specify the antimicrobial used: Erythromycin, Azithromycin, Clarithromycin, etc.]	will be left blank
mic[cepha]		MIC to cephalosporin	Numeric	##.##	MIC to cephalosporin in μg/ml [please specify the antimicrobial used: Cefotaxime, Ceftriaxone, etc]	will be left blank
mic[antimicrobia		MIC to antimicrobial	Numeric	##.##	MIC to different other antimicrobial tested	Please specify the antimicrobial using specific variables

Variable name	Name of the variable in the site specific database	Variable label	Туре	Values and coding	Definition	Comments
nbdosepcv13		Number doses PCV13	Numeric	#	Number doses PCV13	
dosepcv13		PCV13 vaccination	Code	0-no 1-yes 9-unknown	Vaccination with PCV13	
datepcv13		Date of vaccination with first dose PCV	date	dd/mm/yyyy	Date of latest dose PCV	
nbdoseppv		Number doses PPSV23	Numeric	#	Number doses PPSV23	
doseppv		PPSV23 vaccination	Code	0-no 1-yes 9-unknown	Vaccination with PPSV23	
dateppv		Date vaccination with PPSV23	date	dd/mm/yyyy	Date of vaccination with PPSV23 for the latest and previous dose if available	
underdis		Underlying diseases	Code	0-no 1-yes 9-unknown		This variable can be collected as such or by specifying conditions 52-59
underdistype		Underlying diseases by immune status	Code	0-no	Underlying diseases by immune status	For definitions please refer to table 4

Variable name	Name of the variable in the site specific database	Variable label	Туре	Values and coding	Definition	Comments
				1-immunocompetent 2- immunocompromiss ed 9-unknown		
cardiovasc		Cardiovascular diseases	Code	0-no 1-yes 9-unknown	Patient was diagnosed with a chronic cardiovascular disease: see table 4 for ICD codes	
respdis		Respiratory diseases	Code	0-no 1-yes 9-unknown	Patient was diagnosed with a chronic respiratory disease or asthma: see table 4 for ICD codes	
rendis		Renal diseases	Code	0-no 1-yes 9-unknown	Patient was diagnosed with a chronic renal disease including nephrotic syndrome	
immunodef		Immunodeficiency	Code	0-no 1-yes 9-unknown	Patient was diagnosed with an acquired or congenital immunodeficiency	

Variable name	Name of the variable in the site specific database	Variable label	Туре	Values and coding	Definition	Comments
hiv		Human immunodeficiency virus (HIV) disease	Code	0-no 1-yes 9-unknown	See table 4	
leukemia		Lymphoid and myeloid leukaemia; multiple myeloma		0-no 1-yes 9-unknown	See table 4	
lymphoma		Hodgkin lymphoma, Follicular lymphoma, Non-follicular lymphoma, MatureT/NK-cell lymphoma, Other and unspecified types of non-Hodgkin lymphoma		0-no 1-yes 9-unknown	See table 4	
transplant		Solid organ transplat	Code	0-no 1-yes 9-unknown	See table 4	
malignancy		Generalized malignancy	Code	0-no 1-yes 9-unknown	See table 4	

Variable name	Name of the variable in the site specific database	Variable label	Type	Values and coding	Definition	Comments
immunomed		Immunosuppressing medication	Code	0-no 1-yes 9-unknown	See table 4	
diabetes		Diabetes mellitus	Code	0-no 1-yes 9-unknown	Patient was diagnosed with diabetes mellitus type 1 or 2	
asplenia		Asplenia or splenectomised	Code	0-no 1-yes 9-unknown	Patient with functional or anatomical asplenia / splenectomy in the clinical history	
sicklemia		Sickle cell disease	Code	0-no 1-yes 9-unknown	Patient with sickle cell disease in the clinical history Also include: Thalassemia, Other haemoglobinopathies	
csfleak		Cerebrospinal fluid (CSF) leak	Code	0-no 1-yes 9-unknown	See table 4	
cohlear		Cochlear implant	Code	0-no 1-yes 9-unknown	See table 4	

Variable name	Name of the variable in the site specific database	Variable label	Туре	Values and coding	Definition	Comments
alcoholism		Alcoholism	Code	0-no 1-yes 9-unknown	See table 4	
liverdis		Liver chronic disease including cirrhosis	Code	0-no 1-yes 9-unknown	See table 4	
smoking		Cigarette smoking	Code	0-no 1-yes 9-unknown	See table 4	
institutionalised		Institutionalized persons	Code	0-no 1-yes 9-unknown	See table 4	
otherdis		Other underlying disease	Text	string20	Specify other underlying conditions included in the recommendation for PCV/PPV vaccination.	
Fluvac		Influenza vaccination	Code	0-no 1-yes 9-unknown	Influenza vaccination for the current season	

Variable name	Name of the variable in the site specific database	Variable label	Туре	Values and coding	Definition	Comments
Other variables						Please include all other variables collected in the site specific surveillance system

Table 2: ICD codes for case identification Clinical IPD

ICD-9 Code	ICD-10 Code	Diagnosis in Text
038	A40, A41	Streptococcal sepsis; other sepsis
003.1		
995.91		
041	A49	Bacterial infection of unspecified site
320	G00	Bacterial meningitis, not elsewhere classified
711	M00	Pyogenic arthritis
420	130.1	Infective pericarditis
041.09	B95.3	S. pneumoniae as the cause of diseases classified to other chapters
041.09	B95.4	Other Streptococcus as the cause of diseases classified to other chapters
041.00	B95.5	Unspecified Streptococcus as the cause of diseases classified to other chapters
995.91 and 790.7		Sepsis with bacteremia ??

SpCAP		
Pneumococcal pneumonia	481	J13

Table 4: ICD codes for the underlying conditions by immune status

Risk conditions	Description	ICD-9 Code	ICD-10 Code
Immunocompromised persons			
Congenital/acquired immunodeficiency		135, 279	D80-D89
Human immunodeficiency virus (HIV) disease		042	B20-B24
Chronic kidney disease		585	N18
Nephrotic syndrome		581	N04
Leukemia	Lymphoid and myeloid leukaemia; multiple myeloma	203 – 205	C91-C92, C90
Lymphoma	Hodgkin lymphoma, Follicular lymphoma, Non-follicular lymphoma, MatureT/NK-cell lymphoma, Other and unspecified types of non- Hodgkin lymphoma	200 – 202	C81, C82, C83, C84, C85
Generalized malignancy			No specific ICD-10 codes
Immunosuppressing medication			No specific ICD-10 codes
Solid Organ Transplant	Transplanted organ and tissue status	V42	Z94
Functional or anatomical asplenia			
Thalassemia, Sickle cell disorders, Other haemoglobinopathies, Diseases of the spleen (including anatomical asplenia)		282, 289.4-5	D56, D57, D58.2, D73
Immunocompetent persons			

Cerebrospinal fluid (CSF) leak		349.81, 388.61	G96.0
Cochlear implant		431	Z96.1
Chronic heart disease	Chronic ischemic heart disease, Cardiomyopathy, Heart failure	412 – 414, 425, 428	125, 142, 150
Chronic lung disease	Emphysema, Other COPD, Asthma	492, 493	J43, J44, J45
Diabetes mellitus	Type 1 Diabetes, Type 2 Diabetes, Malnutrition-related diabetes, Other specified diabetes, Unspecified diabetes	250	E10, E11, E12, E13, E14
Alcoholism	Mental and behavioral disorders due to use of alcohol, Degeneration of nervous system due to alcohol, Alcoholic polyneuropathy, Alcoholic myopathy, Alcoholic cardiomyopathy, Alcoholic liver disease, Alcoholinduced acute pancreatitis, Alcoholinduced chronic pancreatitis, Maternal care for (suspected) damage to fetus from alcohol,	305, 281, 357.5, 425.5, 535.30-31, 571, 655	F10, G31.2*, G62.1, G72.1*, I42.6, K29.2, K70, K85.2*, K86.0*, O35.4
Chronic liver disease, cirrhosis	Hepatic failure, NES, Chronic hepatitis, NES, Fibrosis and cirrhosis, Other diseases of liver, Malignancy of liver	155, 470 – 474	K72, K73, K74, K76, K76.9, C22

Cigarette smoking	Tobacco use, Mental disorders due to tobacco	300.51 292.89	Z72.0*, F17.2, F17.3*
Institutionalized persons	Nursing homes and long-term facilities		No specific ICD-10 codes
Other ICD codes	Site specific conditions included in the high-risk groups for pneumococcal infection		

